### 6.3.3. Baseline/Day 1 Assessments

All baseline tests and procedures must be completed prior to the receipt of the first dose of study drug(s). Participants screened within 45 days before baseline will be eligible to participate in the study.

Initiation of treatment with study drug(s) should take place on the day of the baseline visit (Day 1).

### Cohorts 1 and 2

- Vital signs
- Weight
- Review AEs
- Review concomitant medications
- Complete physical examination
- 12-Lead ECG (Participants must rest quietly in the supine position for a minimum of 5 minutes prior to the recording)

- Symptoms-directed ophthalmologic examination
- Sample collection for:
  - Safety laboratory tests (hematology and chemistry; coagulation)
  - APRI and FibroTest
  - Quantitative plasma HBV DNA
  - Quantitative HBV serum HBsAg, HBcrAg, HBeAg, and HBV RNA
  - Qualitative HBV serology HBeAg, HBeAb, HBsAg, and HBsAb
  - Serum sample for HBV viral sequencing and genotyping sample (baseline)
  - Sparse PK (sparse PK for SLGN not required for Cohorts 1 and 2 [Group A])
  - Urine pregnancy test (females of childbearing potential only)
  - Urinalysis
  - Estimated CLcr (using Cockcroft-Gault method)

- Perform study drug dispensation, and administration (TAF, as needed, VIR-2218 SC, and SLGN)
- Biomarker Samples: collection of PBMC, whole blood, serum, and plasma samples for biomarker analysis

### 6.4. Randomization

### Viremic Cohort 2 (Group A and B) Only

Participants will be randomized 2:1 into Cohort 2 Group A and B and stratified by HBsAg > or  $\leq 3 \log_{10} IU/mL$ .

### 6.5. Treatment Schedule

### **Cohort 1:**

- Baseline/Day 1, Week 4, and Week 8 SC VIR-2218
- Week 12, 16, and 20 SC VIR-2218; add-on IV nivolumab
- Week 24, 28, and 32 IV nivolumab
- Oral TAF dose daily for 36 weeks
- Oral SLGN dose weekly for 24 weeks, starting Week 12 through Week 35

### **Cohort 2:**

### **Group A:**

- Baseline/Day 1, Weeks 4 and 8 SC VIR-2218
- Weeks 12, 16, and 20 SC VIR-2218; add-on IV nivolumab
- Weeks 24, 28, and 32 IV nivolumab
- Oral SLGN dose weekly for 24 weeks, starting Week 12 through Week 35

### **Group B:**

- Baseline/Day 1, Weeks 4, 8, 12, 16, and 20 IV nivolumab
- Oral SLGN dose weekly for 24 weeks, starting Day 1 through Week 23

### 6.6. Post-Day 1 Treatment Assessments

The post-Day 1 treatment assessments have a visit window of  $\pm$  2 days (except for Weeks 13 and 14 in Cohort 1 and Weeks 1, 2, 13, 14 in Cohort 2), and EOT will have a window of  $\pm$  5 days. Posttreatment assessments include the following, performed in a fasted state at all visits from baseline/Day 1 through EOT or in event of ED, unless specifically noted:

All participants will complete the following post-Day 1 study visits:

Cohort 1: Weeks 4, 8, 12, 13\*, 14, 16, 20, 24, 28, 32, and 36 (EOT)

Cohort 2 Group A: Weeks 4, 8, 12, 13\*, 14, 16, 20, 24, 28, 32, and 36 (EOT)

Cohort 2 Group B: Weeks 1\*, 2, 4, 8, 12, 14, 16, 20, and 24 (EOT)

- Vital signs
- Symptom-directed physical examination (at Weeks 4, 8, 14 to 32, if applicable)
- Complete physical examination (at Weeks 12 and EOT)
- Weight (at Week 12, and EOT)
- Review AEs and concomitant medications (at Weeks 1\*, 2, 4, 8, 12, 13\*, and 14 to EOT)
- 12-lead ECG (Participants must rest quietly in the supine position for a minimum of 5 minutes prior to the recording) (at Weeks 12 and EOT)
- Sample collection for:
  - Safety laboratory tests (hematology and chemistry; coagulation) (at Weeks 4, 8, 12, 14 to EOT)
  - APRI and FibroTest (at Weeks 12, and EOT)
  - Quantitative plasma HBV DNA (at Weeks 4, 8, 12, 14 to EOT)
  - Quantitative HBV serum HBsAg, HBcrAg, HBeAg, and HBV RNA (at Weeks 4, 8, 12, 14 to EOT)
  - Qualitative HBV serology HBeAg, HBeAb, HBsAg, and HBsAb (at Weeks 4, 8, 12, 14 to EOT)
  - Sparse PK samples (Cohorts 1 and 2 [Group A] at Day 1, Weeks 12, 20, and 32; Cohort 2 [Group B] at Weeks 12 and 20)
  - Serum sample for HBV viral sequencing and genotyping sample (at Weeks 4, 8, 12, 14 to EOT)
  - Urinalysis (4, 8, 12, 16 to EOT)
  - Urine pregnancy test (females of childbearing potential only; at Weeks 4, 8, 12, 16, 20, and EOT; and at Weeks 24, 28, and 32, if applicable)
  - Estimated CLcr (using Cockcroft-Gault method) (at Weeks 12 and EOT)
  - Quantification of TSH levels at EOT (Cohort 1 and 2 [Group A], Weeks 24 and 36; Cohort 2 [Group B], Weeks 12 and 24)

### . .

- Ophthalmologic Examination (-4 to +10 days of visit)
  - Cohort 1 and 2 [Group A]: Week 24 and 36
  - Cohort 2 [Group B]: Week 12 and 24 and EOT for participants who stop dosing before Week 24.
  - Symptom-directed ophthalmologic examination (at Weeks 4, 8, 14 to 32, if applicable)
- Study treatment
  - Study drug accountability and review dosing diary
  - Study drug dispensation
  - Study drug administration (Oral TAF, as needed, SC VIR-2218, and oral SLGN)

The following evaluations are to be completed at phone call or virtual visit:

- Review of AEs and concomitant medications
- Review of dosing diary and treatment compliance

### 6.7. Follow-up Assessments

The FU assessments have the following visit windows: Cohort 1: Week 1 ( $\pm$  3 days), Weeks 4 to 16 ( $\pm$  5 days), and Weeks 24 to 48 ( $\pm$  14 days); Cohort 2: Weeks 1 ( $\pm$  2 days), and Weeks 4 to 16 ( $\pm$  5 days), and Weeks 24 to 48 ( $\pm$  14 days). FU assessments include the following:

- All participants will complete following FU visits: Weeks 1\*, 4, 8\*, 12, 16\* (for women of childbearing potential), 24 (Primary), 36, and 48
- Vital signs (at Weeks 4 to 48)
- Symptom-directed physical examination (at Weeks 4 to 48)
- Symptom-directed ophthalmologic examination (at Weeks 4 to 48)

\* Treatment Assessments on Week 1 and Week 13 (Phone Call/Virtual Visit)

- Weight (At Week 48 only)
- 12-lead ECG (At Week 48 only)
- Review AEs and concomitant medications (At Week 1\*, 8\*, 16\*, at Weeks 4 to 48)
- Sample collection for:
  - Safety laboratory tests (hematology and chemistry; coagulation) (at Weeks 4 to 48)
  - APRI and FibroTest (at Weeks 12 and 48)
  - Quantitative plasma HBV DNA (at Weeks 4 to 48)
  - Quantitative HBV serum HBsAg, HBcrAg, HBeAg, and HBV RNA (at Weeks 4 to 48)
  - Qualitative HBV serology HBeAg, HBeAb, HBsAg, and HBsAb (at Weeks 4 to 48)
- Urine pregnancy test (females of childbearing potential only, every 4 weeks through Week 48; Week 8 and Week 16 collection will be a virtual/telephonic visit)
- Serum sample for HBV viral sequencing and genotyping sample (baseline) (at Weeks 4 to 48)
- Estimated CLcr (using Cockcroft-Gault method) (at Week 48 only)

\*FU Visit Week 1, Week 8, and Week 16 (Phone Call/Virtual Visit)

The following evaluations are to be completed at the FU Week 1 phone call or virtual visit:

- Review of AEs and concomitant medications
- Review of laboratory results from EOT visit to determine entry into TFFU

Participants who discontinue the study treatment(s) prematurely will be followed for the reminder of the study according to the defined study visits and procedures.

## 6.8. Immunologic Testing

## 6.8.1. Biomarker Sample Collection During Treatment Period

#### Cohort 1

Baseline/Day 1 (predose), Week 12 (pre-SLGN dose, 4 and 24-72 hours postdose), Week 14 (predose), Week 32 (pre-SLGN dose, 4 and 24-72 hours postdose).

#### Cohort 2

## Group A:

Baseline/Day 1 (predose), Week 12 (pre-SLGN dose, 4 and 24-72 hours postdose), Week 14 (predose), Week 32 (pre-SLGN dose, 4 and 24-72 hours postdose)

## Group B:

Baseline/Day 1 (pre-SLGN dose, 4, and 24-72 hours postdose), Week 2 (predose), Week 20 (pre-SLGN dose, 4, and 24-72 hours postdose)

## 6.8.2. Biomarker Sample Collection During Follow-up

Biomarker samples will be collected at FU Week 24 for Cohorts 1 and 2.

## 6.9. Assessments for Early Discontinuation of Study Treatment

## 6.9.1. Criteria for Discontinuation of Study Treatment

Study treatment(s) that are considered related by the investigator to any of the below event(s) will be held in a participant until resolution of the event:

- Any study drug-related AE  $\geq$  Grade 3
- A confirmed, clinically significant laboratory test abnormality (other than ALT) ≥ Grade 3 considered study drug(s) related by the investigator

Study treatment(s) may be reinitiated following resolution of the above event(s) after discussion with the medical monitor. Study treatment(s) should be restarted in line with their preassigned schedules.

Study treatment(s) that are considered related by the investigator to any of the below events will be permanently discontinued:

- Any on-treatment uveitis, confirmed by ophthalmologic evaluation
- Any confirmed recurrence of study drug—related Grade 3 or 4 (excluding laboratory abnormalities) AE following dose interruption mandates permanent discontinuation of study drug(s)
- Unacceptable toxicity or toxicity that, in the judgment of the investigator, compromises the ability to continue study-specific procedures or is considered not to be in the participant's best interest
- Any study drug-related Grade 4 AE (excluding laboratory abnormalities)
- Any study drug—related ≥ Grade 3 AE not able to be medically managed (eg, nausea with antiemetics)
- Any confirmed study drug-related laboratory abnormality  $\geq$  Grade 3 following rechallenge
- A clinically significant Grade 4 laboratory abnormality
- Virological breakthrough: as defined in Section 2

Additional criteria for permanent discontinuation of study treatment(s):

- Intercurrent illness that would, in the judgment of the investigator, affect assessments of clinical status to a significant degree
- Hepatic disease progression or lack of efficacy defined as participants in Cohorts 1 and 2 (Group A) who do not achieve HBsAg decline ≥ 0.2 log10 IU/mL at Week 12
- Participant requests to discontinue for any reason
- Participant noncompliance
- Pregnancy during the study
- At the discretion of the investigator, Gilead, a regulatory agency or an institutional review board (IRB), or independent ethics committee (IEC).

If a participant discontinues study dosing (eg, as a result of an AE), every attempt should be made to keep the participant in the study and continue to perform the required study-related FU and procedures.

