**Individual Treatment Discontinuation Criteria** 

	Study treatment(s) that are considered related by the investigator to any of the below events will be permanently discontinued:
	
 
Any on treatment uveitis confirmed by ophthalmologic evaluation
 

	• Any confirmed recurrence of study drug—related Grade 3 or 4 (excluding laboratory abnormalities) AE following dose interruption mandates permanent discontinuation of study drug(s)
	
 
Any study drug-related ≥ Grade 3 AE not able to be medically managed (eg, nausea with antiemetics)
 

	
 
Any study drug-related Grade 4 AE (excluding laboratory abnormalities)
 

	• Unacceptable toxicity or toxicity that, in the judgment of the investigator, compromises the ability to continue study specific procedures or is considered not to be in the participant's best interest
	• Any confirmed study drug—related laboratory abnormality ≥ Grade 3 following rechallenge
	A clinically significant Grade 4 laboratory abnormality
	
 
Virological breakthrough as defined in Section 2
 

	Additional criteria for permanent discontinuation of study treatment(s):
	• Intercurrent illness that would, in the judgment of the investigator, affect assessments of clinical status to a significant degree
	
 
Hepatic disease progression or lack of efficacy defined as participants in Cohorts 1 or 2 (Group A), who do not achieve HBsAg decline ≥ 0.2 log10 IU/mL at Week 12
 

	Participant requests to discontinue for any reason
	Participant noncompliance
	Pregnancy during the study
	• At the discretion of the investigator, Gilead, a regulatory agency or an institutional review board (IRB) or independent ethics committee (IEC)
Number of Participants Planned:	Approximately 100 participants

Target Population:	Adult, noncirrhotic, participants with CHB infection who are viremic or virally suppressed on a commercially approved HBV NUC treatment.
Duration of Treatment:	TAF 25-mg tablet will be administered orally once daily for up to 84 weeks, as applicable, in Cohort 1
	VIR-2218 200 mg SC will be administered once every 4 weeks for 24 weeks (6 doses)
	Nivolumab 0.3 mg/kg IV was administered once every 4 weeks for up to 24 weeks (up to 6 doses)
	SLGN 3 mg ( $2 \times 1.5$ -mg tablets) will be administered orally while fasting once a week on the same day for up to 24 weeks (up to 24 doses)

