#### 6.9.2. Criteria for Individual Dose Modification

Dose modification and discontinuation criteria for participants with ALT elevations or flare by treatment and cohort are provided in Section 7.7 Toxicity Management

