## 7.7. Toxicity Management

All clinical and clinically significant laboratory toxicities will be managed according to uniform guidelines detailed in Appendix 11.6.

- Grade 3 and 4 clinically significant laboratory abnormalities should be confirmed by repeat testing within 3 calendar days of receipt of results and before study drug discontinuation, unless such a delay is not consistent with good medical practice
- Clinical events and clinically significant laboratory abnormalities will be graded according to the Table for GSI Grading Scale for Severity of Adverse Events and Laboratory Abnormalities (Appendix 11.5)
- When restarting study drug following resolution of the AE, the study drug should be restarted at full dose or modified dose that is dependent upon discussion with the medical monitor
- Any recurrence of the study drug—related Grade 3 or 4 clinical or clinically significant laboratory AE following dose interruption mandates permanent discontinuation of study drug
- Administration of study drug(s) may be discontinued due to a clinical or laboratory event.
   The medical monitor should be consulted prior to dose discontinuation of study drug(s) unless the investigator believes that immediate action is warranted to ensure the continued safety of the participant
- Any questions regarding toxicity management should be directed to the medical monitor.

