## 7.7.2. Grade 3 Laboratory Abnormality or Clinical Event

- For Grade 3 laboratory abnormality or clinical event, study drug may be continued if the event is considered to be unrelated to study drug
- For any study drug-related, Grade 3 AE, study drug should be held
- For any study drug—related ≥ Grade 3 AE not able to be medically managed (eg, nausea with antiemetics), study drug should be permanently discontinued
- For a confirmed laboratory abnormality, study drug—related Grade 3, study drug would be held until toxicity returns to ≤ Grade 2. If a laboratory abnormality recurs to ≥ Grade 3 following rechallenge, study drug should be permanently discontinued, and the participant managed according to local practice. Recurrence of laboratory abnormalities considered unrelated to study drug may not require permanent discontinuation.

• For a Grade 3 clinical event, or clinically significant laboratory abnormality confirmed by repeat testing within 3 calendar days that is considered to be related to study drug, study drug should be withheld until the toxicity returns to ≤ Grade 2

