## 7.7.3. Grade 4 Laboratory Abnormality or Clinical Event

- For a Grade 4 clinical event or clinically significant Grade 4 laboratory abnormality confirmed by repeat testing within 3 calendar days, the study drug should be permanently discontinued, and the participant managed according to local practice. The participant should be followed as clinically indicated until the laboratory abnormality returns to Day 1 of treatment or is otherwise explained, whichever occurs first. A clinically significant Grade 4 laboratory abnormality that is not confirmed by repeat testing should be managed according to the algorithm for the new toxicity grade.
- A Grade 4 laboratory abnormality or clinical event that is not considered clinically significant by the investigator may also be tested for confirmation and study drug continued at the discretion of the investigator.
- The study drug may be continued without dose interruption for a clinically nonsignificant Grade 4 laboratory abnormality (eg, Grade 4 CK after strenuous exercise or triglyceride elevation that is nonfasting or that can be medically managed).

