## 7.7.5. ALT Elevation or Flare Management on Treatment and Treatment-Free Follow-up

## **On-Treatment ALT Management**

Participants with on-treatment serum ALT elevation  $> 2 \times$  nadir or  $> 2 \times$  baseline value and  $\ge 5 \times$  ULN, with or without associated symptoms should be managed according to the guidance below.

All elevated serum ALT should be confirmed as soon as possible and ideally within 3 days of receipt of results. During the visit, a clinical assessment of the participant should be performed. The assessment should include a physical examination, evaluation of the participant's mental status, and the following laboratory tests:

- Laboratory parameters: serum ALT and AST, total bilirubin, GGT, INR, and serum albumin, alcohol screening
- If the ALT elevation is confirmed, the central clinical laboratory will conduct reflex testing for plasma HBV DNA, serology for HBV (HBsAg, HBsAb, HBeAg and HBeAb), HDV, hepatitis A virus (HAV) IgM, HCV, and HEV
- Liver biopsy may be collected for participants meeting Hy's law (ALT >  $3 \times ULN$  and Total Bilirubin >  $2 \times ULN$ ; AST >  $3 \times ULN$  and Total Bilirubin >  $2 \times ULN$ ) with suspected DILI

Additional confirmatory tests such as HDV RNA, HDV IgM, and HEV RNA may be performed locally as per local regulations after further discussion with the Gilead's Medical Monitor.

Based on the results of the confirmatory tests, the following study treatment modifications are recommended (Table 6).

Table 6. Dose Modification and Monitoring

Liver Toxicity Parameters	Action
Confirmed, ALT $\geq 10 \times ULN$ without evidence of hepatic toxicity as defined below	Cohort 1: Hold VIR-2218 and SLGN treatment. Participant should be monitored weekly or more frequently if clinically indicated until ALT < 5 × ULN. Restarting VIR-2218 and/or SLGN treatment may be considered when ALT < 5 × ULN in discussion with the medical monitor. Study treatment should be restarted in line with the original assigned administration schedule.  Cohort 2: Initiate TAF 25 mg once daily and hold VIR-2218 and SLGN dose. Participant should be monitored weekly or more frequently if clinically indicated until ALT < 5 × ULN. Restarting VIR-2218 and/or SLGN treatment may be considered when ALT < 5 × ULN in discussion with the medical monitor. Study treatment should be restarted in line with the original assigned administration schedule.

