Persistent ALT > 2 × baseline and $\geq$ 5 × ULN without evidence of hepatic toxicity, as defined below	Continue study treatment(s), ALT should be evaluated every 2 weeks or more frequently as clinically needed, until ALT < 5 × ULN
Confirmed ALT > 2 × nadir, with evidence of hepatic toxicity, defined as any one of the following confirmed laboratory abnormalities:  Total bilirubin > 2 × ULN  Elevated INR > 0.5 above baseline AND > ULN  Abnormal serum albumin > 1 g/dL decrease from baseline	Cohort 1: Permanently discontinue study treatment(s) except TAF 25 mg once daily. Participant should be monitored weekly until ALT < 5 × ULN, and total bilirubin, INR, and albumin values return to normal or baseline levels.  Cohort 2: Initiate commercially approved NUC treatment once daily and permanently discontinue study treatment(s). Participant should be monitored weekly until ALT < 5 × ULN, and total bilirubin, albumin, and/or INR values return to normal or baseline levels

ALT = alanine aminotransferase; INR = international normalized ratio; NUC = nucleos(t)ide(s); SLGN = selgantolimod; TAF = tenofovir alafenamide; ULN = upper limit of normal

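### The ALT exemption in the 6.9.1 hold bullet was not carried into the Grade 4 stop bullet, 7.7.2 or 7.7.3, so a drug-related ALT flare without hepatic toxicity gets conflicting dosing instructions

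*Supplement*

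**What the plan says.** Two sets of rules in the protocol can apply to an on-treatment ALT rise.

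*General rules.* Section 6.9.1 first lists events for which related treatment is held. Its laboratory bullet reads "A confirmed, clinically significant laboratory test abnormality (other than ALT) ≥ Grade 3 considered study drug(s) related by the investigator", so ALT is outside that hold. Section 6.9.3 also excludes ALT in its cohort-level hold rule. The permanent-stop list that follows in 6.9.1, repeated in the synopsis, includes "A clinically significant Grade 4 laboratory abnormality" without excluding ALT. For a confirmed, drug-related Grade 3 laboratory abnormality, 7.7.2 says "study drug would be held until toxicity returns to ≤ Grade 2". For Grade 4, 7.7.3 says of a "clinically significant Grade 4 laboratory abnormality confirmed by repeat testing within 3 calendar days, the study drug should be permanently discontinued". Neither subsection mentions ALT. On recurrence, 7.7 says that a drug-related Grade 3 or 4 clinical event or "clinically significant laboratory AE following dose interruption mandates permanent discontinuation of study drug".

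*ALT rules.* Table 6 in Section 7.7.5 (Table 1 in the synopsis) covers ALT by degree of elevation. For confirmed ALT of at least 10 × ULN without hepatic toxicity (row 1), VIR-2218 and SLGN are held, and "Restarting VIR-2218 and/or SLGN treatment may be considered when ALT < 5 × ULN", in discussion with the medical monitor. For persistent ALT above twice baseline and at least 5 × ULN without hepatic toxicity (row 2), the action is "Continue study treatment(s), ALT should be evaluated every 2 weeks or more frequently as clinically needed".

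*Routing.* Section 6.9.2 says that the criteria for "participants with ALT elevations or flare by treatment and cohort are provided in Section 7.7 Toxicity Management". The 7.7.5 lead-in says that such elevations should be managed by the guidance that follows it.

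**The concern.** Someone at a site faced with an ALT flare can find two instructions in the same protocol. At Grade 4 they differ in kind: one leaves a return to treatment open, the other closes it. At Grade 3 one continues and the other interrupts.

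The choice affects what happens to the participant. It also affects how the event is counted. Section 8.6.2 tabulates treatment-emergent events leading to temporary interruption separately from those leading to premature discontinuation, and safety and tolerability is a primary objective. If sites resolve the conflict differently, those tables partly reflect which paragraph was read.

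**Working it through.** The plan has no figure to reproduce here. The check maps the ALT grades onto the Table 6 rows and compares the actions.

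Inputs: Appendix 11.5 grades ALT > 5.00 to 10.00 × ULN as Grade 3 and > 10.00 × ULN as Grade 4. The actions come from Table 6, 6.9.1, 7.7.2 and 7.7.3. The case considered is ALT that is confirmed, clinically significant, judged drug-related and without hepatic toxicity.

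| ALT | Grade | Table 6 | General rules | Result |
|---|---|---|---|---|
| > 5 to < 10 × ULN, persistent, > 2 × baseline | 3 | Row 2: continue | 7.7.2: hold to Grade 2 or lower. The 6.9.1 laboratory hold exempts ALT | Conflict with 7.7.2 |
| Exactly 10 × ULN | 3 | Row 1: hold, restart may be considered at < 5 × ULN | 7.7.2: hold to Grade 2 or lower, i.e. ≤ 5 × ULN | Consistent in effect |
| > 10 × ULN | 4 | Row 1: hold, restart may be considered at < 5 × ULN | 7.7.3 and 6.9.1: permanent stop | Conflict |
| ≥ Grade 3 again after a row 1 hold and restart | 3 or 4 | No row for recurrence | 6.9.1 rechallenge bullet, 7.7 and 7.7.2: permanent stop | Table 6 silent |

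Does any text rank the two sets? Section 6.9.2 points to the whole of 7.7, which contains 7.7.2 and 7.7.3 as well as 7.7.5. The 7.7.5 lead-in says *should*, as 7.7.3 does, and introduces Table 6 as a set of recommended modifications. No sentence says that Table 6 overrides the other rules.

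There is a related gap for TAF. Section 7.7.3 speaks of study drug with no exception and states no relatedness condition. Yet row 1 starts TAF in Cohort 2, and row 3 keeps TAF in Cohort 1 even with hepatic toxicity.

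To show what hangs on the choice for one participant (an illustration, not an estimate), use the Section 6.5 schedule: SLGN weekly in Weeks 12 to 35, so 35 − 12 + 1 = 24 doses, and VIR-2218 on Day 1 and Weeks 4, 8, 12, 16 and 20, so 6 doses. Assume onset just before the Week 16 doses, both drugs judged related, and missed doses not made up.

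- Permanent stop: SLGN 4 of 24 (Weeks 12 to 15), VIR-2218 4 of 6.
- Hold and restart after 2, 4 or 8 weeks: SLGN 24 − 2 = 22, 24 − 4 = 20 or 24 − 8 = 16; VIR-2218 5, 5 or 4.
- Hold without restart: the same doses as a permanent stop.

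Cohort 1 and Group A were each planned at 40, so one participant moved between the interruption and discontinuation tables is 1/40 = 2.5 percentage points.

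**The case against.** The strongest reply is that the intended reading is fairly clear. Section 6.9.2 refers to criteria by treatment and cohort, and within 7.7 only Table 6 is laid out by cohort. The 7.7.5 lead-in sends these elevations to the guidance below it. ALT is set apart in the 6.9.1 hold bullet and in 6.9.3. This stands in part: a reader might infer that nothing in the protocol indicates which rule governs, and that goes too far. Precedence is implied. It is not stated, and because the drafters exempted ALT in one 6.9.1 bullet but not in the permanent-stop list below it, a literal reader can take the omission as deliberate.

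Second, the Grade 4 conflict is conditional. Restart is optional and needs medical-monitor discussion, so holding and never restarting satisfies both texts. If the investigator judges the value not clinically significant, 7.7.3 leaves continuation to discretion. Section 7.7 also asks that the monitor be consulted before discontinuation unless immediate action is needed. All of this stands and limits how far sites can diverge. It does not tell the monitor which text to apply to a clinically significant flare.

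Third, recurrence after rechallenge might be read as another contradiction. The documents do not support that as it stands. Table 6 says nothing about recurrence, and the general rules add one. A conflict appears only if row 2 is reapplied to someone already restarted. Silence still needs filling, because an ALT exemption in 7.7.2 would otherwise cast doubt on its rechallenge sentence.

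**Conclusion.** The point holds as a contradiction between safety rules in two situations: drug-related, clinically significant ALT above 10 × ULN (hold with possible restart against permanent stop), and drug-related ALT above 5 and below 10 × ULN that is persistent and above twice baseline (continue against hold). Both assume confirmation and no hepatic toxicity. The first is the more serious, since one of its two answers is irreversible.

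The documents do not say how often such flares occur, so neither the number of participants affected nor the effect on exposure is known. The dose counts above rest on an assumed onset week and hold length. A reader might infer that the functional cure rate is distorted; the documents do not show this. Participants who stop dosing stay in follow-up where possible and are analysed as assigned in the Full Analysis Set. A reader might also infer that 6.9.1 itself holds dosing for Grade 3 ALT through its laboratory bullet; that bullet exempts ALT, and the Grade 3 conflict is with 7.7.2.

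This should be corrected because it concerns stopping and restarting treatment and costs almost nothing to repair.

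**What to change.** Carry the existing exemption through, in the direction the protocol already implies:

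- Add *other than ALT; see 7.7.5* to the Grade 4 laboratory bullet in 6.9.1 and in the synopsis, and to the laboratory rules in 7.7.2 and 7.7.3.
- State in Tables 1 and 6 whether ALT of Grade 3 or higher that recurs after a row 1 hold and restart means permanent discontinuation, as the 6.9.1 rechallenge bullet, 7.7 and 7.7.2 now say.
- Note in 7.7.3 that TAF continues.

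The cost is a few words in four places, one line in each of two tables and one note. No assessment, visit or analysis is added. For ALT, the first edit confirms the restart and continuation that Table 6 already allows.

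### After a restart from an ALT hold, a second drug-related Grade 3 ALT rise means permanent stop in Sections 6.9.1 and 7.7.2 but continue in Table 6, and no precedence is stated

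*Supplement*

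**What the plan says.** Section 6.9.1 has two lists. The first holds treatment for "A confirmed, clinically significant laboratory test abnormality (other than ALT) ≥ Grade 3 considered study drug(s) related by the investigator", so ALT is carved out of the hold. The second stops treatment permanently and includes "Any confirmed study drug-related laboratory abnormality" of Grade 3 or higher after rechallenge, with no carve-out for ALT. The synopsis repeats both lists.

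Section 6.9.2 redirects ALT cases: "Dose modification and discontinuation criteria for participants with ALT elevations or flare by treatment and cohort are provided in Section 7.7 Toxicity Management".

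Section 7.7 then contains three relevant texts:

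- Its general bullets say that recurrence of a drug-related Grade 3 or 4 "clinical or clinically significant laboratory AE following dose interruption mandates permanent discontinuation of study drug".
- Section 7.7.2 holds drug for a confirmed, drug-related Grade 3 laboratory abnormality and adds: "If a laboratory abnormality recurs to ≥ Grade 3 following rechallenge, study drug should be permanently discontinued". ALT is exempt from neither step.
- Table 6 in Section 7.7.5 (Table 1 in the synopsis) deals with ALT alone. Its first row holds VIR-2218 and selgantolimod (SLGN) at confirmed ALT of 10 × ULN or more with no hepatic toxicity, and says: "Restarting VIR-2218 and/or SLGN treatment may be considered when ALT < 5 × ULN in discussion with the medical monitor". Its second row covers persistent ALT above 2 × baseline and at least 5 × ULN, again with no hepatic toxicity, and says: "Continue study treatment(s), ALT should be evaluated every 2 weeks or more frequently as clinically needed, until ALT < 5 × ULN". Neither row has a separate instruction for a participant who has already been held and restarted.

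**The concern.** The point is the second ALT rise, after a Table 6 hold and restart. If it is confirmed, attributed to study drug, persistent, above 2 × baseline, between 5 and 10 × ULN and free of hepatic toxicity, it meets the condition for a permanent stop and the condition for continuing at the same time. If it reaches 10 × ULN again, it meets the condition for a permanent stop and the condition for another hold with possible restart.

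An investigator can follow the protocol faithfully and do either. What depends on the choice is the remaining exposure to SLGN (and to VIR-2218, if the event comes early enough) and the count of treatment-emergent adverse events leading to discontinuation of study drug, which Section 8.6.2 tabulates.

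**Working it through.** No sample size, power or event count is involved. The check intersects the grading scale with the Table 6 bands and compares the prescribed actions.

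**Inputs**

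- Appendix 11.5, ALT: Grade 2 is > 2.50 to 5.00 × ULN, Grade 3 is > 5.00 to 10.00 × ULN, Grade 4 is > 10.00 × ULN.
- Table 6: hold at ≥ 10 × ULN, restart possible at < 5 × ULN, continue at ≥ 5 × ULN if persistent and > 2 × baseline. A third row stops permanently when hepatic toxicity is present.
- Section 4.3, criterion 2d: screening ALT must be < 2 × ULN in Cohort 1 and < 5 × ULN in Cohort 2.
- Section 6.5: SLGN weekly, Weeks 12 to 35 (24 doses); VIR-2218 at Day 1 and Weeks 4, 8, 12, 16 and 20 (6 doses).

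**Step 1. Actions after a restart** (rise confirmed, drug-related, persistent, > 2 × baseline, no hepatic toxicity)

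| ALT | Grade | 6.9.1 and 7.7.2 | Table 6 |
|---|---|---|---|
| exactly 5 × ULN | 2 | rule not triggered | continue |
| > 5 to < 10 × ULN | 3 | permanent stop | continue |
| exactly 10 × ULN | 3 | permanent stop | hold, restart possible |
| > 10 × ULN | 4 | permanent stop | hold, restart possible |

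The Section 7.7 general bullet sides with the stop when the abnormality is clinically significant. With hepatic toxicity Table 6 also stops, so there is no conflict.

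**Step 2. How much of the 5 to 10 × ULN band is affected.** Let b be baseline ALT in multiples of ULN, taken as close to the screening value. The continue row applies from max(5, 2b) up to 10.

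- Cohort 1: b < 2, so 2b < 4, which is below 5. The whole band is in conflict once the rise is persistent.
- Cohort 2 Group A: b may be anything below 5. For b ≤ 2.5 the whole band is affected. For b = 4 the row starts above 2 × 4 = 8; for b = 4.9 it starts above 2 × 4.9 = 9.8. Between 5 and 2b, with no hepatic toxicity, Table 6 gives no instruction to continue, so stop against continue does not arise there.

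Cohort 2 Group B is not affected, because all its treatment was discontinued (Section 3.2.1).

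**Step 3. First event.** At a first confirmed, drug-related Grade 3 ALT, Section 7.7.2 holds drug because it lacks the exemption given in 6.9.1, while the second row of Table 6 continues. The two disagree before any restart.

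**Step 4. Illustration of size.** Hold at Week 16, restart at Week 20, ALT 6 × ULN confirmed at Week 24. SLGN doses left under Table 6: 35 − 24 + 1 = 12 of 24. Under 6.9.1, if SLGN is a drug considered related: 0. VIR-2218 doses left: 0 either way, since its last dose is at Week 20.

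**The case against.** The strongest reply is that Section 6.9.2 already settles the matter. It sends ALT criteria, including discontinuation, to guidance arranged by treatment and cohort, and within Section 7.7 only Table 6 is arranged by cohort. Also, the restart permission in 6.9.1 refers to events in its own hold list, whose laboratory item excludes ALT, so rechallenge there could mean rechallenge after a non-ALT hold. Both readings are plausible, but neither is stated. Section 6.9.2 points to Section 7.7 as a whole, which holds both rules. Table 6 is introduced as a recommendation, whereas the general bullet is mandatory. The second reading does not help in Section 7.7.2, where the hold that precedes rechallenge has no ALT exclusion.

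Second, the medical monitor is involved in restarts and is normally consulted before discontinuation, which would reduce divergence between sites. That stands, but the monitor works from the same unreconciled text.

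Third, the point overlaps with another conflict. ALT above 10 × ULN is Grade 4 and, if clinically significant, already means a permanent stop under 6.9.1 and 7.7.3, so the restart route is itself disputed. That is a reason to fix both together. An ALT exemption in the Grade 4 bullet alone would leave this conflict in place.

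Three stronger readings are tempting and not supported:

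- A reader might infer that the missing ALT exemption in the rechallenge bullet is a drafting error. Sparing ALT from a first hold while stopping on recurrence is a coherent design, and the documents do not say which was meant.
- A reader might infer that a small drift, such as from 4.9 to just above 5 × ULN, triggers the clash. It does not: the stop needs a confirmed, drug-related abnormality and the continue row a persistent one.
- A reader might infer that the primary analysis is compromised. The Full Analysis Set is analysed as assigned, participants who stop dosing stay in follow-up, and missing counts as failure. The denominator does not change; only the treatment received behind the estimate does.

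**Conclusion.** The contradiction is in the current text and should be mended. For a restarted participant without hepatic toxicity it sets a permanent stop against continuing for ALT > 5 to < 10 × ULN, and a permanent stop against hold with possible restart at 10 × ULN or more. The first clash covers the whole band in Cohort 1 and only the part above 2 × baseline in Cohort 2 Group A. A reader might take it to cover the full band in every cohort, but the baseline condition in Table 6 rules that out. Section 7.7.2 adds a hold-against-continue conflict at the first Grade 3 rise.

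The practical effect depends on timing: up to 12 of 24 SLGN doses in the Week 24 illustration, VIR-2218 only for events before its last dose at Week 20, and the number of adverse events counted as leading to discontinuation. This assumes baseline ALT close to screening ALT and attribution of the rise to the drug in question. The documents give no frequency for the full sequence of flare, recovery, restart and second rise, so the number of participants affected cannot be estimated.

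**What to change.** Reconcile Section 6.9.1 and its synopsis copy, the Section 7.7 general bullets, Section 7.7.2, and Tables 1 and 6 for ALT of Grade 3 or higher, both at the first event and after a restart. Each ALT band should carry one stated action in each situation, including the part of the Cohort 2 band where Table 6 is silent. Add one sentence saying which section governs ALT. Do this together with the related Grade 4 ALT conflict. Which action applies, and whether the rechallenge rule exempts ALT, is for the sponsor to decide.

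The cost is protocol wording only; no new data or procedures are needed.
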